6 HANDLING OF MISSING VALUES

In the case of missing observations, the number and percentage of missing values will be reported. No imputation for missing values will be performed.

7 STATISTICAL METHODOLOGY AND STATISTICAL ANALYSES

7.1 STATISTICAL METHODS

Descriptive analyses will be conducted to evaluate the demographic, clinical and treatment characteristics for the study cohorts defined in Section 4. Results will be

PFIZER CONFIDENTIAL

reported in aggregate. Categorical variables (e.g., ECOG performance status) will be reported as frequency and percentage. Continuous variables such as age will be reported as mean, standard deviation, median and range (minimum-maximum). Chi-square testing will be used to assess associations between categorical variables when patient counts for single cells within the results tables are greater or equal to 5. When distribution cannot be assumed to be Chi-square, then Fisher's exact test will be used. Depending on normality, analysis of variance (ANOVA)/t-tests or Kruskall-Wallis tests will be used for continuous variables. An alpha level of 0.05 will be the primary criterion for statistical significance of this study.

Time-to-event outcomes will be assessed using the Kaplan-Meier method with 95% CIs, and summary tables of the number of events and censored patients at 6, 12, 18, 24, 30, and 36 months.

CCI

To reduce the effect of selection bias, the study team will first consider clinical outcomes compared among propensity score matched cohorts. The propensity score, defined as the probability of being initiated on PB+FUL treatment, will be estimated using a multivariate logistic regression model conditional on the baseline covariates (e.g., age, gender, ethnicity, body mass index (BMI), menopausal status, comorbidities, ECOG, stage of diagnosis, count of metastatic sites and site of metastases). Each individual will have a propensity score that represents the probability of being treated with PB+FUL. Pairs of treated and untreated subjects will be matched on the logit of the propensity score using a caliper of width equal to 0.2 of the standard deviation of the logit of the propensity score, as this caliper has been shown to be optimal in a range of settings. The propensity score will be used to select patients for chart review, as well as the single confounding variable during analysis. 1:n matching could be done by propensity score matching, n could be 1, 2, 3, etc.

Alternatively, if propensity score matching is not supported by the sample size, standardized or normalized inverse probability of treatment weighting (IPTW) using propensity score may be applied to balance baseline demographic and clinical characteristics between the 2 comparison cohorts. For standardized IPTW, the propensity score weight will be calculated as the inverse of the propensity score (1/propensity score), then create a weight reflect the sample size for each of the treatment groups, i.e., $(1/\text{propensity score}) * (\text{number of obs. in treatment A}) / (\text{number of obs. in entire study group})$. For normalized IPTW, the weights will be calculated as the inverse of patients' estimated probability of being in treatment. Finally, the normalized weights will be calculated by dividing each weight by the overall mean weight. After weighting, the sum of weights attributed to each patient in a given cohort may not be equal to the sample size of this cohort, consequently, the effective sample size after weighting may be different than the original sample size (i.e., before weighting), although the total size of whole study population will not be changed.

Last, during analysis, multivariable Cox regression models will be used to further reduce bias associated with underlying characteristics of the patient populations that may affect treatment selection. Specifically, all variables will be fitted into a multivariable Cox proportional hazard regression model to assess independent associations between clinical outcomes and probability of an event (hazard ratio) adjusting for the influence of other variables within the model.

Analyses will be conducted using statistical analysis software 9.4 (SAS®; SAS Institute Inc., Cary, NC, US) and/or R: A Language and Environment for Statistical Computing (R Foundation for Statistical Computing, Vienna, Austria) as appropriate.

An intent-to-treat approach will be taken for the analyses.

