#### Description of patient demographic, clinical and treatment characteristics

Descriptive analyses will be conducted to evaluate the demographic, clinical and treatment characteristics overall, as well as for the cohorts and stratifications defined above. Results will be reported in aggregate. Categorical variables (e.g., ECOG performance status) will be reported as frequency and percentage. Continuous variables such as age will be reported as mean, standard deviation, median and range (minimum-maximum). In the case of missing observations, the number and percentage of missing values will be reported.

---

\* If the SAP is modified, the study protocol will be updated accordingly and re-submitted to the IRB.

All descriptive tables will be presented overall and for each of the Cohorts defined above and, as supported by the final sample size, stratified to present the results for the subgroups defined in **Section 8.2.4**.

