3.1 STATISTICAL HYPOTHESES

The primary objectives of this study are intended to be hypothesis-generating, as such no hypothesis will be tested for these.

PFIZER CONFIDENTIAL

CCI

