3.2 STATISTICAL DECISION RULES

An alpha level of 0.05 will be the primary criterion for statistical significance of this study.

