4.4 SUBGROUPS

* Visits are defined as physical encounters with the practice, detected by vital sign records. The second and third visits must be observed after the index date to demonstrate continuity of care. There is no required time span between the additional visits and the index date.

PFIZER CONFIDENTIAL

As supported by the final sample size, each of the results tables and figures will be stratified to present the data for the following stratifications:

- *Menopausal status (pre-, peri-, and post-menopausal) – post-menopausal only*
- *Metastases (visceral vs. non-visceral, bone only vs. non-bone only)*
- *Metastatic status (de novo versus relapsed/recurrent)*
- *Stage at diagnosis (I/II, III, IV or not documented)*
- *Number of metastatic sites (1, 2 and ≥ 3)*
- *Prior adjuvant endocrine therapy (both prior to and after metastases)*
- *Prior adjuvant chemotherapy (both prior to and after metastases)*
- *Age stratifications (e.g., 18-50, 51-69, ≥ 70) also <65 years and ≥ 65 years*
- *Race (White, Black, other, not documented)*
- *Palbociclib starting dose (75 mg, 100 mg, and 125 mg starting dose)*
- *Eastern Cooperative Oncology Group (ECOG) performance status score (0/1, and 2+) 90 days prior to index*
- *Disease-free interval from end of adjuvant treatment (< 12 months, ≥ 12 months)*

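### SAP 7.1 attaches significance tests at alpha 0.05 to descriptive tables for which SAP 3.1 says nothing will be tested, without naming the groups compared or any multiplicity handling

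*SAP*

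**What the plan says.** - **Position on testing.** SAP 3.1: "The primary objectives of this study are intended to be hypothesis-generating, as such no hypothesis will be tested for these". SAP 2.2 defines the primary objectives as describing (1) baseline patient, provider and clinic characteristics and (2) treatment patterns, in patients who started first-line PB+FUL.
- **Decision rule.** SAP 3.2: "An alpha level of 0.05 will be the primary criterion for statistical significance of this study". SAP 7.1 repeats the sentence. Neither place exempts the primary objectives.
- **Methods.** SAP 7.1 opens: "Descriptive analyses will be conducted to evaluate the demographic, clinical and treatment characteristics for the study cohorts defined in Section 4". Later in the same paragraph it adds: "Chi-square testing will be used to assess associations between categorical variables", provided each table cell holds at least 5 patients. It then names Fisher's exact test as the fallback, and ANOVA/t-tests or Kruskal-Wallis tests for continuous variables.
- **Overview of analyses.** SAP Table 2 (section 7.2.2) lists descriptive statistics as the only method for baseline, provider/clinic and treatment-pattern analyses.
- **Protocol.** The matching paragraph of Protocol 8.7.3 says "Categorical variables (e.g., ECOG performance status) will be reported as frequency and percentage", gives summary statistics for continuous variables, and contains no test and no alpha.
- **Strata.** SAP 4.4 says "each of the results tables and figures will be stratified to present the data for the following stratifications", followed by 12 bullets. This depends on the final sample size, a condition repeated in SAP 7.2.

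**The concern.** The analyses introduced in the first sentence of the SAP 7.1 paragraph are the primary-objective analyses, so the tests that follow apply to them on a plain reading. SAP 3.1 says the opposite. A programmer working from 7.1 would add p-value columns. One working from 3.1 or Table 2 would not.

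The tests also lack what is needed to interpret them. The primary objectives concern a single visible cohort (317 first-line PB+FUL patients in Protocol Table 3), and a test of association needs groups. They could be strata within that cohort or a comparison cohort in redacted text; 7.1 does not say. No multiplicity rule is visible, and nothing labels the p-values as nominal.

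At stake is how the results are described. A study that presents itself as descriptive could report some differences as statistically significant under a study-wide 0.05 rule when they are chance findings from an unplanned set of tests. The descriptive estimates themselves are unaffected.

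**Working it through.** **Step 1: the plan's own figure.** The only error-rate figure stated is alpha = 0.05, identical in SAP 3.2 and 7.1. It is set, not derived, and the SAP gives no number of tests, so there is nothing further to reproduce.

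**Step 2: the texts side by side, for the same tables.**

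| Place | Tests for demographic, clinical and treatment tables? |
|---|---|
| SAP 3.1 | None for the primary objectives |
| SAP 3.2 | Alpha 0.05 for the whole study, no exemption |
| SAP 7.1 | Chi-square, Fisher, ANOVA/t, Kruskal-Wallis at 0.05 |
| SAP Table 2 | Descriptive statistics only |
| Protocol 8.7.3 | Descriptive statistics only |

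Three of the five places point to no tests. SAP 7.1 prescribes them, and SAP 3.2 leaves room for them.

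**Step 3: number of rows that could carry a p-value.** From SAP Table 1, counting reported descriptive variables and leaving out identifiers, pure eligibility items, index regimen, dates and line of therapy:

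- Demographic 11, provider/clinic 4, disease 15, treatment 18: 11 + 4 + 15 + 18 = 48.
- Low count, without treatment variables: 11 + 4 + 15 = 30.
- High count, with the 31 listed comorbidities tested one by one in place of a single comorbidity row: 48 − 1 + 31 = 78.

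**Step 4: one grouping (one cohort against another).** For m tests, the expected number below 0.05 if no difference is real is 0.05 × m. The chance of at least one is 1 − 0.95^m if the tests were independent. They are not (height, weight and BMI, for example), so the last column is illustrative only.

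| m | Expected below 0.05 | Chance of at least one, if independent |
|---|---|---|
| 30 | 1.5 | 0.79 |
| 48 | 2.4 | 0.91 |
| 78 | 3.9 | 0.98 |

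**Step 5: upper scenario, only if tests were run across all 12 bullets of SAP 4.4.** 12 × 30 = 360 to 12 × 78 = 936 tests, with 48 rows giving 12 × 48 = 576. Expected below 0.05 under the same no-difference assumption: 0.05 × 360 = 18 to 0.05 × 936 = 46.8, with 28.8 at 576. This is a loose ceiling, for the reasons given under the objection.

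**Step 6: under SAP 3.1 as written.** The primary-objective tables carry no p-values.

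**The case against.** The strongest counter-argument is that the tests belong to a comparison we cannot see. SAP 7.1 refers to study cohorts in the plural, SAP 2.1.3 contains a redacted second entry, the IPTW paragraph speaks of two comparison cohorts, and redacted text follows the SAP 3.1 disclaimer directly. If the tests serve that comparison, 3.1, 3.2 and 7.1 are compatible in intent. This stands as a possibility, but it does not remove the gap: the visible test sentences are not limited to such a comparison, and they sit in the general descriptive paragraph.

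Protocol 8.7 also allows the SAP to modify the protocol's plans, so the protocol's silence on tests is not in itself a contradiction. That is right. The conflict that matters lies within the SAP, between 7.1 on one side and 3.1 and Table 2 on the other. The table shells are an embedded file that is not available, so p-value columns are not confirmed.

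Two stronger readings are tempting, and the documents do not support them.

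- **A reader might infer that the plan produces hundreds of p-values and dozens of chance findings.** No sentence says tests are run across strata. SAP 4.4 stratifies in order to present data, subject to sample size. The count of 576 also crosses some variables with themselves (race by race, ECOG by ECOG), and the menopausal bullet ends by restricting to post-menopausal patients, which may leave no contrast. A global absence of differences is not credible either, because some pairs are related by definition or biology, such as stage IV at diagnosis with de novo status, or age with menopausal status.
- **A reader might infer that these p-values will be used to judge balance after matching or weighting.** The SAP never says so. It is true only that no balance measure is visible in the propensity-score text of SAP 7.1. The multivariable Cox models described there address outcomes, not baseline balance.

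**Conclusion.** The inconsistency is real. SAP 7.1 prescribes significance tests at 0.05 for tables that SAP 3.1 says involve no testing and that SAP Table 2 treats as descriptive. The groups compared and the handling of multiplicity are not stated in the visible text.

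If the rule is applied as written to one cohort comparison, it gives about 30 to 78 unadjusted p-values, with 1.5 to 3.9 expected below 0.05 if no difference is real. Several hundred is an upper scenario that requires testing across all the SAP 4.4 strata. These figures rest on counting each Table 1 variable as one test (comorbidities separately in the high count) and on the no-difference assumption. The expected counts do not need independence; the family-wise figures do.

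The point should be fixed before the tables are produced. It threatens the labelling of results, not the estimates, and no visible decision or sample size depends on these p-values. Whether the tests were meant for a redacted comparison cannot be settled from the documents.

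**What to change.** 1. In SAP 7.1, remove the tests from the primary-objective (first-line PB+FUL) tables. Report n (%), mean/SD and median/range, with 95% CIs for key proportions. With 317 patients, the half-width for a proportion of 50% is about 1.96 × √(0.5 × 0.5 / 317) = 0.055, or 5.5 percentage points, which tells the reader more than a p-value would.
2. In SAP 3.2 and 7.1, limit the tests and the alpha 0.05 statement to a named, pre-stated comparison, and say which groups it compares. Label any other p-values nominal and exploratory.
3. For any matched or weighted two-cohort baseline table, report standardized mean differences before and after adjustment instead of p-values. A p-value depends on sample size as well as imbalance, so a smaller matched sample can look balanced when it is not.
4. Check that SAP 3.1, 3.2, 7.1, Table 2 and the table shells then say the same thing.

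Cost: SAP wording and simpler table shells, with no new data. The downside is that the descriptive tables have no p-value columns. If the tests were always meant only for a separate comparison, one limiting sentence in 7.1, with the matching limit in 3.2, settles the conflict in items 1 and 2.

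### SAP 7.1 sets its chi-square threshold of 5 on observed instead of expected cell counts, and its fallback to Fisher's exact test has no criterion

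*SAP*

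**What the plan says.** SAP 7.1, in its paragraph on descriptive analyses, uses chi-square for associations between categorical variables "when patient counts for single cells within the results tables are greater or equal to 5". It continues: "When distribution cannot be assumed to be Chi-square, then Fisher's exact test will be used". No number is attached to that second sentence, and expected counts are mentioned nowhere in the protocol or SAP.

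SAP 3.2 sets the level, and 7.1 repeats it: "An alpha level of 0.05 will be the primary criterion for statistical significance of this study". Neither section says whether tests are two-sided, and 7.1 does not say whether chi-square carries a continuity correction.

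Three other places bear on how far the rule reaches:

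- SAP 3.1: "The primary objectives of this study are intended to be hypothesis-generating, as such no hypothesis will be tested for these".
- SAP 4.4: if the sample size supports it, "each of the results tables and figures will be stratified to present the data for the following stratifications". The list includes palbociclib starting dose, ECOG 0/1 against 2+, and race.
- SAP Table 2 names only descriptive statistics and Kaplan-Meier methods.

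**The concern.** The familiar threshold of 5 is a check on expected counts, because these govern how well the chi-square distribution approximates the test statistic. Applied to observed counts, the choice of test depends on the result itself. If a small group is expected to have about three patients with a characteristic, chi-square becomes available only when five or more are seen, that is, when there is an excess. In the other direction, an observed count below 5 triggers Fisher's exact test even if the expected count is comfortably above 5.

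At stake is which side of 0.05 some descriptive p-values fall on. No estimate, endpoint definition or Kaplan-Meier analysis is affected.

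**Working it through.** The plan states no attained error rate for this rule, so there is no figure to reproduce. The check compares the SAP rule with the same rule based on expected counts.

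**Inputs**
- N = 317: final first-line PB+FUL count, Protocol Table 3.
- Level 0.05: SAP 3.2 and 7.1; two-sided is assumed.
- Group splits and prevalences: assumptions, since the documents give no stratum sizes or category frequencies.
- Chi-square: Pearson without continuity correction first, then with it. Fisher: two-sided.

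**Step 1: why the direction matters.** In a 2x2 table with m patients having the characteristic (the less common category), the smallest expected count is n_small × m / N. For 20 of 317 to reach an expected count of 5, m must be at least 5 × 317 / 20 = 79.25. At 15% prevalence the small group expects 20 × 0.15 = 3.0 patients; for 40 patients at 8% it expects 40 × 0.08 = 3.2. All observed cells reach 5 only when the small group is well above that.

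**Step 2: two tables where the choice changes the verdict**
- *7/20 vs 46/297.* Observed cells 7, 13, 46 and 251 are all at least 5, so the SAP rule gives chi-square. Smallest expected count: 20 × 53 / 317 = 3.3. X² = 317 × (7×251 − 13×46)² / (20 × 297 × 53 × 264) = 5.12, p = 0.024. Fisher gives p = 0.055.
- *3/87 vs 24/230.* One observed cell is 3, so the SAP rule gives Fisher, p = 0.068. Smallest expected count: 87 × 27 / 317 = 7.4. X² = 317 × (3×206 − 84×24)² / (87 × 230 × 27 × 290) = 3.95, p = 0.047.

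**Step 3: error rates under no difference.** For each pair of counts (a, c), the null probability is Bin(a; n₁, π) × Bin(c; n₂, π). These are summed over all tables with p < 0.05, separately for an excess and a deficit in the small group.

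| Split, prevalence | Chi-square used with an expected count below 5 | SAP rule: excess / deficit | Expected-count rule: excess / deficit |
|---|---|---|---|
| 277 vs 40, 8% | 21.1% of tables | 3.61% / 0.61% | 2.50% / 0.61% |
| 297 vs 20, 15% | 17.0% | 3.56% / 0.39% | 2.50% / 0.39% |
| 220 vs 97, 8% | 1.4% | 2.9% / 1.6% | 2.9% / 2.1% |
| 220 vs 97, 15% | about 0% | 2.7% / 2.2% | 2.7% / 2.2% |

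In the first two rows the rule adds 3.61 − 2.50 = 1.11 and 3.56 − 2.50 = 1.06 percentage points for an excess, and nothing for a deficit. The SAP-rule totals are about 4.2% and 4.0%. At 297 vs 20 the ratio of excess to deficit is 3.56 / 0.39, about 9 to 1, but it is already 2.50 / 0.39, about 6 to 1, under the expected-count rule.

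**Step 4: sensitivity**
- *Continuity correction.* With corrected chi-square under the same observed-count trigger, excess rejections are 1.9% (277 vs 40) and 1.8% (297 vs 20), both below 2.5%. The Step 2 tables give corrected p = 0.051 and 0.078, both on Fisher's side of 0.05.
- *Equal groups.* The expected count is then (a + c) / 2, which cannot be below 5 if a and c are both at least 5. The rule is only over-conservative: total error is 2.67% against 5.04% for 20 vs 20 at 30%, and 2.47% against 4.20% for 30 vs 30 at 20%.
- *Wider sweep.* Over 81 scenarios with N = 317 (small group 10 to 80, prevalence 3% to 40%), the largest total error is 5.10% under both rules. The largest error in one direction is 3.74% under the SAP rule and 3.09% under the expected-count rule.

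**The case against.** The strongest case against has four parts.

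- **The fallback sentence may already cover this.** A table with an expected count of 3.3 could reasonably go to Fisher's exact test as one whose distribution is not chi-square. That reading is open, so it cannot be said flatly that the plan will use chi-square where it is invalid. But such a table meets both sentences, and nothing says which prevails. Nor does the fallback restore chi-square where observed counts are below 5 and expected counts are adequate.
- **No affected test is clearly announced.** SAP 4.4 has tables stratified to present data and does not call for tests between strata. SAP 7.1 ties the descriptive analyses to the cohorts in Section 4, where the comparison cohort is redacted and its size unknown. SAP 3.1 and Table 2 point away from testing. This stands, and it limits the point to wherever the tests are in fact run.
- **The lopsidedness is mostly not the rule's doing.** A reader might infer that the rule creates the imbalance between excess and deficit, or inflates the overall error rate. The calculation supports neither: most of the imbalance remains under the expected-count rule, and the largest total error in the sweep is the same under both.
- **The rise depends on using uncorrected chi-square.** The SAP does not specify this, and the rise is gone with a correction. This also stands, and is itself a reason to specify the correction.

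**Conclusion.** The point holds in a limited form. The only numerical trigger in SAP 7.1 is on observed counts, which is the wrong quantity, and the fallback does not supply the right one. With uncorrected chi-square and a small group set against a much larger one, the rule raises null rejections for an excess by about one percentage point, from 2.5% to 3.6%, in the two very unequal splits. It can also withhold chi-square where expected counts are adequate: at 220 vs 97 and 8% prevalence this lowers deficit rejections from 2.1% to 1.6%. Individual verdicts near 0.05 can change in either direction.

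These sizes rest on assumed splits and prevalences, two-sided tests and 2x2 tables only. The redacted comparison could not be assessed. The consequence is minor: descriptive p-values near 0.05, wherever these tests are run. It is a wording correction worth making, not a threat to the study's conclusions.

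**What to change.** Replace the two sentences in SAP 7.1 with a single rule: *Chi-square will be used when all expected cell counts under independence are at least 5; otherwise Fisher's exact test will be used.* Add whether chi-square is computed with or without a continuity correction. Using Fisher's exact test for every categorical comparison that is kept would also remove the ambiguity, at the price of some conservatism.

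The cost is one phrase in the SAP and no new data. Standard software already prints expected counts.

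### The standardized IPTW formula, applied as printed to comparator patients, does not balance the two cohorts

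*SAP*

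**What the plan says.** SAP 7.1 introduces the score in these terms: "The propensity score, defined as the probability of being initiated on PB+FUL treatment". It adds that "Each individual will have a propensity score that represents the probability of being treated with PB+FUL". A comparator patient's score is therefore also a PB+FUL probability.

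Weighting is a fallback, used "if propensity score matching is not supported by the sample size", and it "may be applied to balance baseline demographic and clinical characteristics between the 2 comparison cohorts". Two versions are offered.

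- **Standardized.** The plan states that "the propensity score weight will be calculated as the inverse of the propensity score (1/propensity score" in parentheses, and "then create a weight reflect the sample size for each of the treatment groups". The expression printed is the reciprocal of the score times the number in treatment A divided by the number in the whole study group.
- **Normalized.** Here "the weights will be calculated as the inverse of patients' estimated probability of being in treatment", and each weight is then divided by the overall mean weight.

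The paragraph ends by noting that the weighted size of a cohort may differ from its actual size, "although the total size of whole study population will not be changed".

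Protocol 8.7.3 (Clinical outcomes) has the same score definition and the same formula. Neither document prints 1/(1 − score) or refers to the probability of the treatment received.

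**The concern.** Inverse probability weighting balances two cohorts when each patient is weighted by the reciprocal of the probability of the treatment that patient received. With a score e defined as the probability of PB+FUL, this is 1/e for PB+FUL and 1/(1 − e) for the comparator. The plan prints only the first.

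The half for PB+FUL is right. A programmer who follows the text for the comparator would give the largest weights to the comparator patients least like the PB+FUL cohort, which is the reverse of what is needed. Weighted baseline tables and weighted Kaplan-Meier curves, if produced, would then carry the original confounding, or more of it, while being presented as adjusted. Protocol Table 1 schedules adjusted outcomes analyses, and this paragraph is the visible specification for the weighting.

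**Working it through.** The plan gives no numerical result for the weights. The check is whether the printed formula achieves the balance stated as its purpose.

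**1. Algebra.** Let f(x) be the covariate distribution in the combined population and e(x) the probability of PB+FUL.

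- PB+FUL patients have density proportional to f(x)·e(x). Multiplying by 1/e(x) returns f(x).
- Comparator patients have density proportional to f(x)·(1 − e(x)). Multiplying by 1/e(x) gives f(x)·(1 − e(x))/e(x), which is not f(x) unless e is constant. Multiplying by 1/(1 − e(x)) returns f(x).
- The factor n/N is constant within a cohort, so it cannot change that cohort's weighted mean. Using each cohort's own n/N leaves the imbalance unchanged.

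**2. Worked example.** Inputs: 317 first-line PB+FUL patients (Protocol Table 3); 200 comparators (assumed, since the count is redacted); one binary confounder with prevalence 60% in PB+FUL and 40% in the comparator (assumed). N = 517.

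| | PB+FUL | Comparator | e = PB+FUL/total |
|---|---|---|---|
| Confounder present | 190.2 | 80 | 190.2/270.2 = 0.704 |
| Confounder absent | 126.8 | 120 | 126.8/246.8 = 0.514 |

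- Unweighted standardised difference: (0.6 − 0.4)/√[(0.24 + 0.24)/2] = 0.408.
- Weight 1/e, PB+FUL: 190.2/0.704 = 270.2 and 126.8/0.514 = 246.8, so prevalence is 270.2/517 = 0.523.
- Weight 1/e, comparator: 80/0.704 = 113.6 and 120/0.514 = 233.6, so prevalence is 113.6/347.2 = 0.327.
- Standardised difference with the printed weight: (0.523 − 0.327)/√[(0.523·0.477 + 0.327·0.673)/2] = 0.403.
- Weight 1/(1 − e), comparator: 80/0.296 = 270.2 and 120/0.486 = 246.8, so prevalence is 0.523 and the difference is 0.

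Sum of weights: the printed formula gives 317.0 + 347.2 × 317/517 = 529.9; with own-group n/N it gives 317.0 + 347.2 × 200/517 = 451.3; the correct form gives 317 + 200 = 517.

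**3. Other assumed patterns.** The same calculation with comparators of 100, 200 and 317:

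| Prevalence, PB+FUL vs comparator | Unweighted | Printed weight (100 / 200 / 317) | Correct weight |
|---|---|---|---|
| 60% vs 40% | 0.408 | 0.406 / 0.403 / 0.400 | 0 |
| 30% vs 10% | 0.516 | 0.474 / 0.446 / 0.422 | 0 |
| 10% vs 30% | −0.516 | −0.592 / −0.624 / −0.643 | 0 |

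The normalized option has the same imbalance as the printed weight if its probability is read as the PB+FUL score, and none if it is read as the probability of the treatment received.

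**4. Two covariates.** With two independent binary covariates (each 50%, log-odds 0.7 and 1.2, comparator 200), the standardised differences go from 0.324 to 0.346 and from 0.590 to 0.581. Correct weights give 0 for both.

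**5. Fitted score.** Two normal covariates with log-odds slopes of 0.6, the score estimated by logistic regression, comparator 200, 1000 simulated data sets:

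| | Mean standardised difference | Sum of weights, median (range); N = 517 |
|---|---|---|
| Unweighted | 0.54 / 0.53 | – |
| Printed weight | 0.63 / 0.62 | 582.9 (532.3–704.8) |
| Correct standardized weight | 0.00 / 0.00 | 516.6 (507.1–534.2) |

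Correctly defined normalized weights sum to exactly 517.0.

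**The case against.** The best defence is that the formula is a loose template. It says treatment A rather than PB+FUL, refers to each treatment group, and sits under a method whose name implies the treatment received. On that reading one would repeat the expression for the second group with that group's probability, and the result would be correct. An experienced programmer might well do so. What stands is that group-specific weights were probably intended. But the section defines the score explicitly as the PB+FUL probability for every individual, and the only group-specific term printed is n/N, which has no effect on balance. The correct weight is reached only by departing from the text.

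The defence is also right about reach. Harm requires that matching proves infeasible, that weighting is used, that the standardized version is chosen (or the normalized one misread), and that the formula is followed literally. A multivariable Cox model follows and, if correctly specified, could still give a valid hazard ratio. It would not repair weighted baseline tables or survival curves. The comparator and the comparative objective are redacted, and the table shells cannot be seen, so it is unknown whether such outputs are planned.

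Finally, the remark about unchanged total size follows the normalized description, for which it holds exactly. The totals above are therefore a reason to clarify that sentence, not a separate error.

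**Conclusion.** The concern holds. Under the plan's own definition of the score, the printed standardized weight is wrong for comparator patients and fails the stated purpose of balancing the cohorts. This follows from algebra whenever the score varies with covariates and does not depend on the examples.

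The size does depend on assumptions: the comparator count is redacted and the confounder patterns are invented. Across the single-confounder patterns tried, the standardised difference after the printed weight ranged from modestly smaller than unweighted (0.516 to 0.422) to clearly larger (−0.516 to −0.643). These figures illustrate the mechanism and do not estimate bias in this study.

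The defect is confined to an optional fallback for the between-cohort comparison. The first-line PB+FUL descriptive and Kaplan-Meier analyses are untouched. It should be corrected before any weighted analysis is programmed.

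**What to change.** In SAP 7.1 and Protocol 8.7.3, with PS the probability of PB+FUL:

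- State the standardized weight as (n of PB+FUL/N)/PS for PB+FUL patients and (n of comparator/N)/(1 − PS) for comparator patients.
- Define the normalized weight as the reciprocal of the estimated probability of the treatment the patient actually received, divided by the overall mean weight.
- Say that the total weighted size equals N exactly for normalized weights and approximately for standardized weights.

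The cost is wording in the two documents. No new data are needed.
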